6.8.1.3 Supportive/sensitivity analyses

IPA as measured by VerifyNow® will also be summarized as a continuous variable.

Those summaries will be provided considering the available PD assessment time points (baseline, 15, 30, and 60 min post dose).

A mixed model to assess treatment effect at 30 min. from start of treatment injection on platelet reactivity as measured by VerifyNow®, i.e., PRU value, will be performed using subject as a random factor, and treatment (8 mg, and 16 mg), age (continuous), sex (male, female), and time from onset of symptoms to study treatment administration (continuous, hours), as fixed factors.

Assuming relevant number of subjects (i.e., ≥ 10 subjects) in each STEMI/NSTEMI subgroup, the consistency across STEMI and NSTEMI subgroups will be assessed by testing the interaction effect of STEMI/NSTEMI with study treatment dose in the primary endpoint analysis. Logistic regression analysis of the PD response will be performed using ACT-246475 dose (8 mg vs 16 mg), ST-segment elevation (STEMI vs NSTEMI), age (continuous), and gender (male vs female) as covariates.

The same analysis as described in the main analysis section will be performed on the additional PD response within the 1st hour endpoint using the FAS.

The main analysis, on the PD response, and PD response within the 1st hour, will be repeated on the PPS if the PPS is at least 10% smaller than the mFAS.

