#### ***10.3.3.4 Supportive/sensitivity analyses***

Assuming relevant number of subjects in each STEMI/NSTEMI subgroup, the consistency across STEMI and NSTEMI subgroups will be assessed by testing the interaction effect of STEMI/NSTEMI with treatment dose on the primary endpoint analysis.

A logistic regression analysis of the PD response will be performed using subject, ACT-246475 dose (8 mg, and 16 mg), ST-segment elevation (STEMI vs NSTEMI), age (continuous), gender (male, female) as covariates.

Further analyses will be described in the SAP as necessary.

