6.8.1.1 Variable

The primary pharmacodynamic (PD) endpoint is the *PD response* that is defined for each subject as a PRU < 100 at 30 min after study drug injection, as measured via VerifyNow[®].

The primary PD variable (PRU_{30m}) is the platelet reactivity as measured by VerifyNow[®] at 30 min after study drug injection [see the table of assessments in the protocol, table 2].

The analysis variable of the PD response is defined as follows for a given subject:

$$\begin{aligned} & \text{IF } PRU_{30m} < 100 \\ & \text{THEN } PD \text{ response} = \text{YES} \\ & \text{ELSE } PD \text{ response} = \text{NO} \end{aligned}$$

PRU time is based on planned time point and not on the actual collection time.

Supportive primary PD endpoint

The following endpoint is not described in the protocol and has been added. The main purpose is to assess the effect of the two study treatment doses, when relaxing the time of a PRU < 100, i.e., considering as a response a PRU < 100 at 15, 30 or 60 min. post injection.

This endpoint is defined as per the following algorithm and will describe the subject's *PD response within the 1st hour*:

*IF minimum of (PRU_{15m}, PRU_{30m}, PRU_{60m}) < 100
THEN PD response within 1st hour = YES
ELSE PD response within 1st hour = NO*

Where PRU_{15m}, PRU_{30m}, and PRU_{60m} refer to PRU measured by VerifyNow® at 15, 30, and 60 minutes after study drug administration.

PRU time is based on planned time point and not on the actual collection time.

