6.8.1.2 Analysis

The analyses described in this section consider the primary endpoint, i.e., PD response. Sensitivity analysis of the PD endpoints will be described in Section 6.8.1.3.

Unless stated otherwise, all analyses will be conducted on the mFAS.

Hypotheses and statistical model

The primary objective is to assess IPA 30 min after a single s.c. injection of ACT-246475 in subjects with AMI receiving conventional antithrombotic treatment (e.g., aspirin, oral P2Y₁₂ receptor antagonists, anticoagulants).

To achieve this objective, the testing strategy will be to test the study treatment effect (using the proportion *p* of responders, i.e., achieving PRU < 100 at 30 minutes post-injection) for each of the two doses, considering the following hypotheses:

$$H_{0HD}: p_{HD} \leq 50\% \text{ vs } H_{1HD}: p_{HD} \geq 85\%$$

$$H_{0LD}: p_{LD} \leq 50\% \text{ vs } H_{1LD}: p_{LD} \geq 85\%$$

where LD is the lower ACT-246475 dose (8 mg), and HD the higher ACT-246475 dose (16 mg).

Each of the two null hypotheses will be tested by a two-sided z-test at a significance level (alpha) of 0.025, which is an overall level of 0.05 for the study level and adjusted for multiplicity using Bonferroni method.

Main analysis

The primary statistical analysis will be performed on the mFAS population for each dose level.

It will be based on the study treatment received (which may differ from the assigned one).

The analysis of the primary endpoint will be performed for each of the two doses independently, i.e., considering 2 null hypotheses (proportion of patients achieving a

response is less than or equal to 50%) at 0.025 type I error each [see protocol section 10.3.3.1].

The study will be declared positive for the primary objective, if at least 1 out of the 2 null hypotheses is rejected at 0.025 type I error level.

A one-sided z-test will be computed and the 95% CI of the proportion of responders will be provided.

A summary of response, in terms of number (%) of responding subjects, will be provided.

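### The 30-minute PRU model puts a random subject effect on one value per subject, so the two variances cannot be separated and the dose inference rests on unstated software choices

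*SAP*

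**What the plan says.** SAP 6.8.1.3 introduces "A mixed model to assess treatment effect at 30 min. from start of treatment injection on platelet reactivity as measured by VerifyNow®, i.e., PRU value". It continues that the model "will be performed using subject as a random factor, and treatment (8 mg, and 16 mg), age (continuous), sex (male, female", closing the list with "and time from onset of symptoms to study treatment administration (continuous, hours), as fixed factors". No assessment-time term, dose-by-time term, covariance structure or degrees-of-freedom method is given. SAP section 8 names only the software, SAS 9.4 or higher.

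SAP 6.8.1.1 defines the 30-minute variable: it "is the platelet reactivity as measured by VerifyNow[®] at 30 min after study drug injection", and "PRU time is based on planned time point and not on the actual collection time". The default set in SAP 6.8.1.2 is stated as "Unless stated otherwise, all analyses will be conducted on the mFAS", and SAP 4.1.4 admits a subject to the mFAS only if the 30-minute PRU exists. SAP 6.8.1.3 names no other set for this model.

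The repeated-measures analysis is a separate model in SAP 6.8.2.2. It also has subject as a random factor, but it uses PRU at 15, 30 and 60 minutes, lists assessment time as a fixed factor and adjusts for baseline PRU.

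**The concern.** A random subject effect separates variation between subjects from variation within them. That needs more than one value from at least some subjects. Here there is one value each, so the data cannot divide the total variance into its two parts.

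The trial is meant to support the choice of dose for Phase 3 (Protocol 3.2 and 4.2). The primary tests compare each dose with 50%, not with the other dose. The logistic regression in SAP 6.8.1.3 compares the doses, but on the dichotomised response. The 30-minute PRU model is the one planned model that compares them on the continuous scale at the primary time point alone. As specified, whether it returns a p-value and confidence interval depends on how the programmer codes subject and which degrees-of-freedom method is used.

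**Working it through.** **Inputs**
- Evaluable subjects: 21 per arm, 42 in total (Protocol 10.5).
- Values per subject: one 30-minute PRU (SAP 6.8.1.1, 4.1.4).
- Fixed effects: intercept, dose, age, sex, onset-to-dosing time, so 5 columns (SAP 6.8.1.3).
- Covariate and outcome values: simulated, as an assumption. The ranks and the identifiability result do not depend on them.

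**The plan's own figure.** The documents give no sample size or degrees of freedom for this model; N = 42 comes from the primary test. For a one-sample z-test with the null variance under H0, n = [(z_a √(p0 q0) + z_b √(p1 q1)) / (p1 − p0)]². With two-sided alpha 0.025, 90% power, p0 = 0.50 and p1 = 0.85:

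n = [(2.2414 × 0.5 + 1.2816 × 0.3571) / 0.35]² = 20.34, so 21 per arm (power 91.2% at 21). The stated figure reproduces.

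**Step 1: covariance.** V = σ²_subject ZZ′ + σ²_residual I. With one row per subject, Z = I, so V = (σ²_subject + σ²_residual) I. Only the sum appears. This is algebra and holds for any N and any coding of subject.

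**Step 2: likelihood.** In one simulated data set (total variance 4134.9), each split of that total gave the same fit:

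| Share assigned to subject | −2 REML log-likelihood | Dose estimate | SE |
|---|---|---|---|
| 0% | 433.6097 | −57.68 | 20.33 |
| 10% | 433.6097 | −57.68 | 20.33 |
| 50% | 433.6097 | −57.68 | 20.33 |
| 90% | 433.6097 | −57.68 | 20.33 |
| 99.9% | 433.6097 | −57.68 | 20.33 |

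The ordinary linear model gives the same estimate and SE. All four entries of the information matrix for the two variances equal 0.5 × 37 / 4134.9² = 1.082 × 10⁻⁶, so its rank is 1, not 2.

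**Step 3: degrees of freedom for dose, N = 42**

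| Specification | Calculation | df |
|---|---|---|
| Subject entered as written, containment | N − rank[X Z] = 42 − 42 | 0 |
| Subject nested in treatment, containment | rank[X Z] − rank[X] = 42 − 5 | 37 |
| No random term | N − rank[X] = 42 − 5 | 37 |

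In the second row, age, sex and onset time would still have 0.

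**Step 4: contrast with repeated values.** If all 42 subjects have values at 15, 30 and 60 minutes, and assessment time is added as a three-level factor, there are 126 records. Then rank[X] = 5 + 2 = 7, rank[X Z] = 42 + 2 = 44, and the residual df are 126 − 44 = 82. The subject variance is now identifiable. Adding baseline PRU, as SAP 6.8.2.2 does, leaves rank[X Z] at 44 because it is constant within subject.

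**The case against.** The best defence is that little is lost. Only the total variance matters to the dose contrast, so the estimate and SE match those of the ordinary linear model. A blank p-value or a software warning would be seen at once. No alpha or study-success rule rests on this model, and the trial is exploratory. All of that stands, and it limits the severity.

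Several stronger readings are tempting but not supported:

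- **That the dose test has no degrees of freedom, full stop.** The SAP names no degrees-of-freedom method and gives no code. Zero follows only under containment with subject un-nested. In this parallel-group design, nesting subject in treatment gives 37 for dose, and residual or between-within methods could also give usable values.
- **That the model will fail to converge.** The calculation evaluates the likelihood at fixed variance splits. It shows a flat ridge, not a failed fit.
- **That this is the only dose comparison on continuous PRU.** The longitudinal model in SAP 6.8.2.2 also gives one. Having no dose-by-time term, its dose effect is common to 15, 30 and 60 minutes. Only a model specific to 30 minutes is unique to SAP 6.8.1.3.
- **That Protocol 10.3.3.4 carries the same live defect.** There, "A logistic regression analysis of the PD response will be performed using subject, ACT-246475 dose" and further covariates. Subject as a logistic covariate is a different error, and the SAP's logistic model already omits it. What remains is that SAP section 11 does not record the change, which is a documentation matter.
- **That the model was meant to use all time points.** No time term is listed, and SAP 6.8.2.2 already holds that analysis.

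None of this rescues the random term, because the two variances cannot be separated under any coding.

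**Conclusion.** The point holds, and it is minor. The subject and residual variances in the 30-minute model are not separately identifiable, and the reported inference for dose can range from 0 to 37 degrees of freedom according to choices the SAP does not state. The dose estimate, its REML standard error, the primary responder tests and the sample size are unaffected.

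This rests on one 30-minute PRU per subject, which follows from the SAP's variable definition, and on 42 evaluable subjects. With a different N, the as-written containment result is still zero and the ordinary linear model has N − 5.

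**What to change.** In SAP 6.8.1.3, remove subject as a random factor from the 30-minute model. Specify instead an ordinary linear model of 30-minute PRU in the mFAS on dose, age, sex and time from symptom onset to dosing. Report the adjusted 8 mg minus 16 mg mean difference with a 95% CI on the residual degrees of freedom (37 with 42 subjects). Keep the random subject effect only in the longitudinal model of SAP 6.8.2.2.

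The same edit could state whether the omission of baseline PRU is intended, since SAP 6.8.2.2 includes it. Adding it would leave 36 degrees of freedom.

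The cost is one sentence. Data collection, sample size and the primary analysis do not change, and nothing estimable is lost.

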### 1.3 Purpose and rationale of the study

ACT-246475 is a potent, short-acting, reversible, and selective antagonist of the platelet P2Y12 receptor to be administered subcutaneously. ACT-246475 has shown a favorable PK/PD and safety profile in animal models, confirmed in studies conducted in healthy subjects. This Phase 2 study is complementary to study ID-076A201, which is being conducted in patients with stable coronary artery disease (CAD) to assess the PD, PK, tolerability and safety of a single s.c. injection of ACT-246475. AMI may be associated with sympathetic activation and subsequent peripheral vasoconstriction which might affect the uptake of ACT-246475 after s.c. administration and consequently its onset of action. This study will generate complementary data to assess whether the onset of action of ACT-246475 is affected in a population of patients with AMI. The impact of the 2 different doses on the PD and PK of ACT-246475 when administered on top of standard of care for AMI (e.g., antiplatelet and anticoagulant therapies) will be assessed in this study. The two doses will be the same as the ones evaluated in study ID-076A201.

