6.8.1.4 Subgroup analyses

The protocol does not plan any analysis by subgroup, however the study treatment effect across the following subgroups will be explored by repeating the main analysis on primary PD endpoint, assuming there are enough subjects, i.e., ≥ 10 subjects by subgroup.

- Age: < 55 vs ≥ 55 years
- BMI: < 25.0 vs (≥ 25.0 and < 30.0) vs ≥ 30.0 kg/m²
- Sex: male vs female
- Diabetes mellitus at baseline: yes vs no

- Chronic kidney disease: yes vs no

PTs to consider for identification of subjects with/without diabetes mellitus, or chronic kidney disease, are described in Section 5.4.4.

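### Consistency across STEMI and NSTEMI is judged by a dose-by-MI-type interaction that cannot respond to an equal shortfall at both doses; the planned MI-type main effect can, but is not named as the measure.

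*SAP*

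**What the plan says.** Protocol 10.3.3.4 states that "the consistency across STEMI and NSTEMI subgroups will be assessed by testing the interaction effect of STEMI/NSTEMI with treatment dose". SAP 6.8.1.3 carries this over, with consistency to be "assessed by testing the interaction effect of STEMI/NSTEMI with study treatment dose in the primary endpoint analysis", and adds a size condition: "Assuming relevant number of subjects (i.e., ≥ 10 subjects) in each STEMI/NSTEMI subgroup".

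The next sentence in both documents plans a logistic regression of the 30-minute response. In the SAP its terms are dose plus "ST-segment elevation (STEMI vs NSTEMI), age (continuous), and gender (male vs female) as covariates". MI type is a main effect there, and no interaction term is listed.

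The primary analysis (SAP 6.8.1.2) is a separate one-sample test of the response rate against 50% for each dose, with STEMI and NSTEMI together. There is no placebo arm (protocol 3.2).

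SAP 6.8.1.4 adds subgroups in which the treatment effect "will be explored by repeating the main analysis on primary PD endpoint": age, BMI, sex, diabetes and chronic kidney disease. SAP 6.8.2.4 uses the same list for the other PD endpoints. MI type is in neither.

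**The concern.** SAP 6.8.1.2 defines the treatment effect as the proportion of responders at each dose. A consistent effect across MI types therefore means similar response rates in STEMI and NSTEMI. The interaction addresses a different question: whether the difference between the two doses changes with MI type. A drug that worked poorly in one MI type at both doses would leave that difference unchanged.

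The risk is in how the report would read. A non-significant interaction is the stated evidence of consistency, so the report could call the effect consistent on that basis although one MI type responds well below the 85% target. Protocol 3.2 and 4.2 say the results will support the choice of the Phase 3 dose, so a reader would want to see the response rate in each MI type.

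**Working it through.** **Inputs from the documents.** 21 evaluable subjects per arm, 42 in total; 50% under the null and 85% under the alternative; alpha 0.025 per dose; 90% power (protocol 10.5). Allocation 1:1. At least 10 subjects in each MI type for the interaction test (SAP 6.8.1.3).

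**Assumptions, because the documents do not give them.** The MI-type split (21:21, 28:14 or 32:10), the response rates by MI type, and a two-sided 5% level for the interaction and main-effect tests. Age and sex are left out of the logistic model.

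**Step 1: the plan's own figure.** One-sample z-test with the null variance in the critical value:

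n = [(z_a·√(p0·q0) + z_b·√(p1·q1)) / (p1 − p0)]²

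With two-sided 0.025, z_a = 2.241 and z_b = 1.282:

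n = [(2.241 × 0.5 + 1.282 × 0.357) / 0.35]² = 20.34, so 21. The stated 21 per arm is reproduced. At n = 21 this test rejects with 16 or more responders.

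**Step 2: algebra of the interaction.** Let response be 85% in one MI type and 50% in the other, at both doses.

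- MI-type odds ratio at 8 mg: (0.85/0.15) / (0.50/0.50) = 5.67.
- MI-type odds ratio at 16 mg: 5.67.
- Interaction odds ratio: 5.67 / 5.67 = 1.

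The interaction null is exactly true, however large the common deficit. No sample size would give the test power against it.

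**Step 3: simulated rejection rates.** 20,000 trials per scenario, 42 subjects, likelihood-ratio tests at 5%, the same rates at both doses. In the uneven splits the smaller group is the poor responder. The last column is the chance that at least one dose reaches 16/21.

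| Response by MI type | Split | Interaction | MI-type main effect | At least one dose positive |
|---|---|---|---|---|
| 85% vs 50% | 21:21 | 7.4% | 73% | 45% |
| 85% vs 50% | 28:14 | 8.4% | 69% | 74% |
| 85% vs 50% | 32:10 | 8.6% | 59% | 87% |
| 95% vs 60% | 21:21 | 3% to 4% | about 85% | 90% |

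When both MI types respond at 85%, the interaction test rejects in 7.2%, 8.1% and 7.0% for the three splits. This small-sample size is somewhat above nominal, and the 85% vs 50% rows barely differ from it. The main-effect test also has a size of about 7% at 85% vs 85%, so its power is slightly flattered. A Wald version of the interaction test rejects in under 2% of trials at 85% vs 50%.

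Fisher's exact test on pooled doses, which is not planned, rejects in 58% at 85% vs 50% and about 75% at 95% vs 60% (near-equal split). The planned logistic main effect does better in both.

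**Step 4: the interaction against its own target.** If response is 50% in one MI type at one dose only and 85% in the other three cells (21:21 split), the interaction test rejects in about 23%. It is weak even for the pattern it is meant to find.

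**Step 5: precision of rates by MI type.** Exact 95% CIs: 5/10 gives 19% to 81%; 11/21 gives 30% to 74%.

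**The case against.** The strongest reply is that the same paragraph already covers the gap. With no control arm, the STEMI vs NSTEMI coefficient in the planned logistic regression is the dose-adjusted comparison of response between MI types, and Step 3 shows it has useful power. This stands. A reader might infer that the SAP would miss a deficit in one MI type; the documents do not support that. What is missing is the designation: the consistency sentence points to the interaction, not to this coefficient.

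Four other stronger readings are tempting.

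- **That MI type is the trial's main stratum.** The rationale in protocol 1.3 concerns AMI as a whole, "which might affect the uptake of ACT-246475 after s.c. administration". It does not suggest that uptake differs between STEMI and NSTEMI. Protocol 4.2 treats the two as one population, and the randomization in 5.1.3.1 names no stratification.
- **That SAP 6.8.1.4 misdescribes the protocol** when it says "The protocol does not plan any analysis by subgroup". The sentence introduces repetition of the main analysis within subgroups, which the protocol does not plan. Protocol 10.3.3.4 plans an interaction test and a covariate model, and both are kept in SAP 6.8.1.3.
- **That no response rate by MI type will be produced.** SAP section 12 places the complete output list in a separate appendix that is not among these documents. Only its absence from the SAP text can be stated.
- **That the gap would reliably be found once the measure is changed.** The response rates and splits are assumptions. With smaller gaps power falls: the pooled Fisher test rejects in 33% at 60% vs 85% and 25% at 70% vs 90%.

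**Conclusion.** The point holds in a limited form. As a stated criterion for consistency, the dose-by-MI-type interaction answers the wrong question, and it has no power beyond its size against an equal deficit at both doses. This part is algebra and rests on no assumption about rates or splits. The rejection rates of about 3% to 4% and 7%, and the main-effect power of about 85% and 73%, rest on the assumed response rates, a near-equal MI-type split, a 5% level and a model without age and sex. Over the splits examined at 85% vs 50%, main-effect power runs from 59% to 73%.

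The SAP already plans a model that can show such a deficit, so this is a matter of naming the right measure and reporting rates by MI type, not of a missing analysis. It concerns a supportive analysis in an exploratory study. The two primary tests and the rule for declaring the study positive are unaffected.

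**What to change.** In SAP 6.8.1.3, base consistency on the dose-adjusted STEMI vs NSTEMI effect on 30-minute response, with its 95% CI. This can be the main effect in the planned logistic regression or the risk difference stratified by dose. Keep the interaction as a descriptive result only.

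In SAP 6.8.1.4, add MI type (STEMI vs NSTEMI) under the same rule of at least 10 subjects, and report n/N, % and the exact 95% CI per dose and pooled. SAP 6.8.2.4 then picks it up through its cross-reference.

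The cost is SAP wording and one extra table. MI type is already collected (protocol 7.2.1, SAP 5.4.5). The intervals will be wide, as Step 5 shows, and the report must say so: a wide interval that includes no difference is not evidence of consistency.

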### **10.5 Sample size**

The computation of the sample size was performed using East 6.0 software (version 6.4.0.1, 30 August 2016) from Cytel Inc.

The sample size is based on the study primary objective of assessing IPA 30 min after ACT-246475 administration, as assessed by the proportion of subjects achieving a response (i.e., PRU < 100 at 30 min post study drug administration). The sample size should be sufficient to allow the rejection at least one of the null hypotheses.

The study should include 21 subjects evaluable for the primary PD endpoint in each arm considering:

- an overall two-sided type I error of 0.05, adjusted for multiplicity using the Bonferroni method for each of the 2 null hypotheses (testing each dose at an alpha level of 0.025),
- a power of 90%, and
- the following assumptions for the response rate under the null and alternative hypotheses as reported in the table below.

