6.8.2.2 Analyses

Summary statistics will be provided for the PD endpoint variable *PRU_{60m} status*, and individual data will be listed. It will be analyzed similarly to the primary PD endpoint in Section 6.8.1.2, and will use the same factors.

A longitudinal analysis of the study treatment effect, on *PD profile over time* will be performed using a mixed model with PRU as the dependent variable, subject as a random factor, and study treatment (ACT-246475 8 mg, and ACT-246475 16 mg), PRU level at baseline, time from onset of symptoms to study treatment administration (continuous, hours), age (continuous), sex (male, female), and assessment time (15, 30 and 60 minutes) as fixed factors.

The proportion of subjects with PRU < 100 by assessment time (0 to 60 minutes) will be plotted as bar charts.

Descriptive statistics of PRU relative change from baseline at each time point will be provided, where change from baseline is defined as the ratio of $([PRU \text{ at time } t - PRU \text{ pre-dose}] / PRU \text{ pre-dose})$ expressed in percentage.

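### STEMI/NSTEMI is left out of both continuous PRU models, although the logistic model of the 30-minute response adjusts the same dose comparison for it

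*SAP*

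**What the plan says.** MI type enters two analyses in SAP 6.8.1.3, both on the binary response PRU < 100 at 30 minutes:

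- a test of the interaction between dose and STEMI/NSTEMI, if each MI type has at least 10 subjects;
- a logistic model: "Logistic regression analysis of the PD response will be performed using ACT-246475 dose (8 mg vs 16 mg), ST-segment elevation (STEMI vs NSTEMI", plus age and gender.

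Both carry over from protocol 10.3.3.4.

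PRU itself is modelled twice:

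- The 30-minute mixed model (SAP 6.8.1.3) has a random subject effect; the other terms listed are "treatment (8 mg, and 16 mg), age (continuous), sex (male, female), and time from onset of symptoms to study treatment administration (continuous, hours), as fixed".
- The longitudinal mixed model (SAP 6.8.2.2) also has a random subject effect. Besides dose, its fixed terms are "PRU level at baseline, time from onset of symptoms to study treatment administration (continuous, hours), age (continuous), sex (male, female), and assessment time".

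MI type is in neither. The subgroup list in SAP 6.8.1.4, reused for the PRU profile in 6.8.2.4, also omits it. Otherwise MI type is only tabulated as a characteristic of the qualifying infarction (SAP 5.4.5). SAP section 11 gives no reason for the difference.

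**The concern.** Age and sex are in all three models. MI type is in the binary one only. The same dose question is therefore adjusted for MI type on one scale and not on the other, which looks like an oversight.

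Two things follow. First, nobody will see a modelled STEMI minus NSTEMI difference in PRU, although PRU is measured at 15, 30 and 60 minutes and MI type is collected. Secondly, protocol 5.1.3.1 describes sealed envelopes opened in sequence and mentions no stratification by MI type. If the arms happen to differ in STEMI share and MI type affects PRU, part of that effect passes into the PRU dose contrast. Protocol 3.2 and 4.2 say the results will help choose the Phase 3 dose.

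**Working it through.** **1. Number of subjects.** Inputs from protocol 10.5 and SAP 6.8.1.2: response 50% under the null and 85% under the alternative, "a power of 90%, and" 0.025 per dose. SAP 6.8.1.2 states: "Each of the two null hypotheses will be tested by a two-sided z-test at a significance level (alpha) of 0.025". With the null variance,

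n = [(z₀.₉₈₇₅·√(0.5·0.5) + z₀.₉₀·√(0.85·0.15)) / 0.35]² = [(2.241·0.5 + 1.282·0.357) / 0.35]² = 20.34, so 21 per arm and 42 in total.

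The plan's figure reproduces. (The same SAP section also says "A one-sided z-test will be computed and the 95% CI of the proportion of responders will be provided". That conflict is a separate matter, and 42 is used below.) At 85% response, about 42 × 0.15 = 6.3 subjects are non-responders.

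**2. Chance imbalance in MI type.** The STEMI share is not given, so 10, 21 and 30 of 42 were tried. With 21 per arm and K STEMI subjects in total, the number x in one arm is hypergeometric. A difference of at least 4/21 = 19 points means |2x − K| ≥ 4.

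| K | Probability |
|---|---|
| 10 | 0.28 |
| 21 | 0.22 (K is odd, so the smallest qualifying difference is 5/21) |
| 30 | 0.31 |

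**3. What that imbalance does.** Assume true response of 75% and 95% in the two MI types and normal PRU with a common SD of 40 to 80. The documents give no SD. The PRU gap between types is d = z₀.₉₅ − z₀.₇₅ = 1.645 − 0.674 = 0.97 SD.

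- A 4/21 imbalance moves the dose contrast by 0.97 × 4/21 = 0.185 SD, or about 7 to 15 units before flooring at 0.
- The standard error of the contrast is √(2/21) = 0.309 SD, so the shift is about 0.185/0.309 = 0.6 standard errors.
- At a 21/21 split of MI types, leaving the factor out raises residual variance by 0.25 × 0.97² = 0.235, so the standard error is about √1.235 = 1.11 times as large.
- Over repeated randomisation the unadjusted dose test stays valid. In simulation with no dose effect (SD 60), it rejected in 5.4% of trials.

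**4. Power for an MI-type difference, PRU against binary.** Two-sided 5% test of the MI-type main effect, 75% against 95% response.

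| Assumed PRU behaviour | STEMI/NSTEMI | PRU t-test | Binary likelihood-ratio test |
|---|---|---|---|
| Graded normal shift, floored at 0, SD 40–80 | 21/21 | 76–86% | 50–53% |
| Same | 10/32 | 71–75% | 40% |
| Same | 30/12 | 62–79% | 45–48% |
| Mixture: MI type changes only the responder share | 21/21 | 33–42% | about 50% |
| Same | 30/12 | 17–21% | 45–48% |

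In the mixture, responders are low and skewed (exponential, scale 15–40, capped at 99) and non-responders are spread from 100 up to 200–300. The likelihood-ratio test is slightly oversized (6–7% under no difference).

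The gain in the graded case has a simple source. For a normal shift at 85% response, the cut-point keeps φ(1.036)²/(0.85 × 0.15) = 0.0544/0.1275 = 43% of the information. That formula does not apply to the mixture.

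**The case against.** The strongest reply is that this is a choice of covariates in supportive models of an exploratory study. The SAP delivers both MI-type analyses that the protocol promised, dose is randomised, and the primary analysis tests each dose separately against 50%. All of that stands, and it limits the point to a low-cost improvement.

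Four stronger readings are tempting, and the documents do not support them:

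- **That analysing MI type on the binary scale must lose much power.** The documents give neither the spread nor the shape of PRU. In healthy subjects both doses reached a mean IPA of at least 90% at 30 minutes (protocol 5.1.1), which suggests that responders may cluster at low values. In that case the PRU comparison can be the weaker one.
- **That the PRU difference should be the main evidence on consistency.** Protocol 10.3.3.4 and SAP 6.8.1.3 define consistency as the dose by MI-type interaction. An additive MI-type term assumes the same dose effect in both types, so it cannot test that.
- **That the study's rationale requires a STEMI/NSTEMI contrast.** Protocol 1.3 says: "This study will generate complementary data to assess whether the onset of action of ACT-246475 is affected in a population of patients with AMI". That concerns AMI as a whole, alongside the study in stable coronary disease. No objective or endpoint compares MI types.
- **That MI type certainly enters only at 30 minutes.** SAP 6.8.2.2 analyses 60-minute status with the factors of 6.8.1.2, which lists none. If the logistic covariates were meant, MI type would also enter there, though still on the binary scale.

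**Conclusion.** The omission and the inconsistency hold on the text alone: MI type adjusts the dose comparison on the binary scale and is missing from both PRU models. As a result no planned model gives a STEMI minus NSTEMI difference in PRU, and the PRU dose contrasts are exposed to chance imbalance. An imbalance of 19 points or more has a probability of about 22 to 31% for the STEMI shares tried. Under the assumed 75% versus 95% response it would move the contrast by about 0.6 standard errors.

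A reader might infer that the PRU dose contrasts are biased. They are not biased systematically, because dose is randomised. What is lost is precision and protection in a single small trial. The primary test is unaffected.

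A power gain for detecting an MI-type difference cannot be promised. It is about 15 to 35 points if MI type shifts PRU in a graded way. It is nil or negative, at the 21/21 and 30/12 splits checked, if MI type changes only how many subjects fail to respond.

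**What to change.** In SAP 6.8.1.3 and 6.8.2.2, add ST-segment elevation (STEMI vs NSTEMI) as a fixed factor to the 30-minute PRU model and to the longitudinal PRU model. From the 30-minute model, report the adjusted STEMI minus NSTEMI difference in PRU with its 95% CI. In the longitudinal model, a single MI-type term would give only an average over 15 to 60 minutes.

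Label this result as supportive and place it beside the planned logistic regression and dose by MI-type interaction. Leave those and the primary test as they are.

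The cost is SAP wording and one degree of freedom per model. MI type is already recorded on the eCRF (protocol 7.2.1). No protocol change or extra subjects are needed.
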